6.0 Regulatory and ethical compliance

This study was designed and shall be implemented and reported in accordance with the criteria of the “European Network Centres for Pharmacoepidemiology and Pharmacovigilance (ENCePP) study” and follows the ENCePP Code of Conduct (EMA 2014). Once a final version of the protocol has been agreed and reviewed by the advisory group, this study will be registered with www.encepp.eu.

7.0 Data dissemination

Initial results will be presented in poster and/or oral format at The Respiratory Effectiveness Group’s (REG) International Summit. At least one manuscript containing more detailed results and methodology will be submitted to a journal specialising in respiratory medicine. Submission for publications will be made as soon as the analyses are completed and the results are verified.

10.0 Timelines

Action	Timeline
Protocol final definition	1 week
Data extraction	1 weeks
Baseline analysis (stage I)	2 weeks
Baseline report writing	2 weeks
Outcome analysis (stage II)	4 weeks
Final report writing	7 weeks
First draft of paper	4-6 weeks from final report

12.0 APPENDIX

12.1 Appendix 1: Definitions

Variable Name	Description	Time Period
Year of COPD diagnosis	Year of First COPD diagnosis	n/a
IDD Cohort	Year of first COPD diagnosis split into three cohorts: 1997 -2001, 2002 - 2006, 2007 - 2010	n/a
Age	Age at COPD diagnosis	n/a
Gender	Gender of patient: Male, Female	n/a
Smoking Status	Smoking status recorded in routine medical notes closest to date of COPD diagnosis	Closest to date of COPD diagnosis
Body Mass Index (BMI)	BMI defined as: Underweight = < 18.499, Normal = $\geq 18.50 - 24.99$, Overweight = ≥ 25.00 , Obese = ≥ 30.00	Closest to date of COPD diagnosis
Exacerbation Rate	Exacerbations were defined as: (i) COPD-related hospital admissions or Emergency Department attendance; (ii) use of acute oral steroids; (iii) General practitioner consultations for lower respiratory tract infections. Two exacerbations occurring within 2 weeks of one another were counted only once.	Calculated during the year prior to and including the date of COPD diagnosis.
mMRC Score	mMRC scores were based on the 5-point 162 scale of the British Medical Research Council questionnaire assessing perceived breathlessness. Combined mMRC score from either routine medical notes or questionnaire data if available.	Closest to date of COPD diagnosis
Lung Function Group	Lung function grade was calculated using GOLD Stage 1, 2, 3 and 4 criteria	Closest to date of COPD diagnosis
Asthma Diagnosis	Presence / absence of a co-morbid diagnosis of Asthma in routine medical notes	Closest to date of COPD diagnosis
Rhinitis Diagnosis	Presence / absence of a co-morbid diagnosis of Rhinitis in routine medical notes	Closest to date of COPD diagnosis
Gastroesophageal reflux disease (GERD)	Presence / absence of a co-morbid diagnosis of GERD in routine medical notes	Closest to date of COPD diagnosis
Heart Failure	Presence / absence of a co-morbid diagnosis of Heart Failure in routine medical notes	Closest to date of COPD diagnosis
Chronic Kidney Disease	Presence / absence of a co-morbid diagnosis of Chronic Kidney Disease in routine medical notes	Closest to date of COPD diagnosis
Osteoporosis	Presence / absence of a co-morbid diagnosis of Osteoporosis in routine medical notes	Closest to date of COPD diagnosis

Diabetes	Presence / absence of a co-morbid diagnosis of Diabetes in routine medical notes	Closest to date of COPD diagnosis
Anxiety - Depression	Presence / absence of a co-morbid diagnosis of Anxiety - Depression in routine medical notes	Closest to date of COPD diagnosis
Chronic Renal Failure	Presence / absence of a co-morbid diagnosis of Chronic Renal Failure in routine medical notes	Closest to date of COPD diagnosis
Ischaemic Heart Disease	Presence / absence of a co-morbid diagnosis of Ischaemic Heart Disease in routine medical notes	Closest to date of COPD diagnosis

Table 1: Full list of demographic, baseline and outcome variables to be examined in the study

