2.2 Study design

A retrospective observational database study using the Optimum Patient Care Research Database. The data utilised in this study ranges from 1997 – 2013. Eligible patients must have a minimum of one year of data prior to their initial date of COPD diagnosis for baseline period, and a minimum of two years of data post their initial COPD diagnosis for outcome period to assess patient characteristics and pharmacological treatment prescriptions.

Cohorts will be chosen to assess how prescription patterns have changed over time and if certain factors such as the introduction of QoF1 in 2004 and Tiotropium (LAMA) becoming licensed in UK in January 2002 influence prescribing behaviour.

Patients will be split into three cohorts based on their date of initial COPD diagnosis:

- 1997 – 2001
- 2002 – 2006
- 2007 – 2010

COPD initial therapy will be defined as pharmacological therapy prescribed during one year prior to and at the initial date of COPD diagnosis (baseline period). COPD therapies will be grouped by treatment class:

- Inhaled corticosteroid (ICS),
- long-acting β_2 -agonist (LABA),
- long-acting muscarinic antagonist (LAMA),
- short-acting β_2 -agonist (SABA),
- short-acting muscarinic antagonist (SAMA) (in single, dual or triple therapy)
- Other respiratory pharmacological therapies (theophylline)
- None (no prior baseline pharmacological therapy).

To identify possible drivers of treatment choice, analyses will be conducted in subgroups according to:

- Year of initial COPD diagnosis
- Comorbid asthma diagnosis
- Lung function grade (GOLD stage 1, 2, 3 or 4 [2])
- mMRC dyspnea scale score
- Baseline exacerbation rate.

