3.0 Study population

3.1 Inclusion and exclusion criteria

Inclusion criteria

COPD diagnosis with QoF approved read codes

Age \geq 40 years

Patients have one year of practice data prior COPD diagnosis and 2 years of practice data after COPD diagnosis

Spirometry data supportive of a COPD dx in the 5 year window around date of diagnosis.

Patients must be diagnosed within the last 15years

Exclusion criteria

Patients aged less than 40 at diagnosis

No valid spirometry data available

Patients diagnosed earlier than 1997

Table 1: Inclusion and exclusion criteria

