5.4 Analysis of study outcomes

COPD initial treatment patterns

Logistic regression analysis for all patients receiving first COPD therapy. This analysis will be conducted on:

- a. All patients receiving first COPD therapy
- b. The subgroup of patients who receive their first therapy on their date of COPD diagnosis

This will be carried out as follows:

Investigate the COPD therapy distribution of by the following main potential predictors:

- a. Year of initial COPD diagnosis (1997-2001; 2002-2006; 2007-2010)
- b. Presence of co-morbid asthma diagnosis
- c. Lung function grade (please note that GOLD stage 2 will be used as the reference). This will also be repeated for the earlier analysis investigating predictors of initial therapy choice for all patients receiving first COPD therapy
- d. mMRC score
- e. Annual exacerbation rates
- f. GOLD group with the following comparisons:
 - B vs A
 - D vs C
 - A+B vs C+D

For each potential predictor consider:

- the distribution of initial COPD therapy (number and percentage of patients and bar chart) will be summarised
- Need to test to see if it varies among the categories of each potential predictor with a chi-square.

Predictors of initial COPD treatment

Evaluate how the potential predictors outlined above could affect the choice of initial COPD therapy in terms of:

a. Odds of being prescribed any initial COPD therapy vs. no therapy

For each potential predictor:

- The distribution of initial COPD therapy (yes/no) (number and percentage of patients and bar chart) will be summarised and a test to see if it varies among the categories of each potential predictor with a chi-square will be completed.
- Odds ratios (ORs) with their 95% confidence intervals (CIs) will be calculated using an univariable logistic regression model and a multivariable logistic regression model with stepwise reduction to derive best-fitting model of non-collinear predictors
- Presence of co-morbid asthma diagnosis used both as adjustment and as stratification variable (two multivariable models)
- Collinearity analysis on all potential predictors and confounders

b. Odds of receiving initial COPD maintenance therapy vs. short-acting agents/no therapy

For each potential predictor:

- The distribution of initial COPD maintenance therapy (yes/no) (number and percentage of patients and bar chart) will be summarised and tested to see if it varies among the categories of each potential predictor with a chi-square.

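### Predictors are not required to precede the prescription: exacerbations share the outcome's window, and mMRC, lung grade and comorbidities use the nearest record with no on-or-before limit

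*Protocol*

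**What the plan says.** - **Outcome.** Protocol section 2.2 defines initial therapy as "pharmacological therapy prescribed during one year prior to and at the initial date of COPD diagnosis (baseline period".
- **Exacerbation rate.** Appendix 1 (section 12.1) gives its time period as "Calculated during the year prior to and including the date of COPD diagnosis".
- **Lung grade, mMRC, asthma and other comorbidities.** In Appendix 1 each is taken "closest to date of COPD diagnosis". For mMRC the source is "Combined mMRC score from either routine medical notes or questionnaire data if available", without a date limit.
- **Spirometry for eligibility.** Section 3.1 asks for "Spirometry data supportive of a COPD dx in the 5 year window around date of diagnosis".
- **Records after diagnosis.** Section 2.2 requires "a minimum of two years of data post their initial COPD diagnosis for outcome period", so every eligible patient has later records from which a nearest value could be drawn.
- **Use.** Section 5.4 enters these variables in logistic regression under the instruction "Evaluate how the potential predictors outlined above could affect the choice of initial COPD therapy in terms of". It runs the analysis on all patients and also on "The subgroup of patients who receive their first therapy on their date of COPD diagnosis".

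**The concern.** The study asks what leads a GP to prescribe. An odds ratio can speak to that only if the predictor describes the patient before the prescribing decision. The protocol's timing rules do not ensure this. An exacerbation that follows treatment, or a breathlessness score that treatment has already altered, can stand in the model as a reason for that treatment. Even a value recorded on the diagnosis date is post-treatment for a patient first prescribed earlier in the baseline year.

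Of the six main predictors in section 5.4, only year of diagnosis is free of the problem. GOLD group A to D has no timing in Appendix 1; if it is built from exacerbations, symptoms and lung function, it inherits the fault. At stake is whether the primary odds ratios can be read as drivers of choice or only as associations.

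**Working it through.** The protocol gives no figure on this point to reproduce. The check compares the windows and then gauges possible size on stated assumptions.

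**1. Windows side by side**

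| Variable | Window | Bound to the prescription date? |
|---|---|---|
| Initial therapy (outcome) | Year before diagnosis, plus diagnosis date | – |
| Exacerbation rate | Year before diagnosis, plus diagnosis date | No; overlap 12 of 12 months |
| Lung grade | Nearest record; eligibility ensures one within the 5-year spirometry window | No |
| mMRC, asthma, other comorbidities | Nearest record; no direction or maximum distance stated | No |

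That the window extends after diagnosis is explicit only for spirometry, which may lie around the date. For the others it follows from a nearest-record rule with no restriction.

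**2. Share of the exacerbation window after treatment.** For a first prescription m months before diagnosis the share is m/12:
- m = 3: 3/12 = 25%
- m = 6: 6/12 = 50%
- m = 9: 9/12 = 75%

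If first prescriptions were uniform over the year (assumption), the average share is 50%. If half were issued on the diagnosis date, it is 0.5 × 0 + 0.5 × 50% = 25%.

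**3. Effect on the exacerbation odds ratio.** All inputs here are assumed: prescribing is independent of earlier exacerbations (true OR 1.0), first prescription uniform over the year, exacerbation rate λ = 0.3 to 1.0 per year, rate multiplied by RR after therapy, and 50% to 90% of patients treated. With Poisson counts,
- untreated: P(0) = exp(−λ)
- treated: P(0) = exp(−λRR) × [1 − exp(−λ(1 − RR))] / [λ(1 − RR)]

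For λ = 0.5 and RR = 0.6, treated P(0) = 0.7408 × 0.1813/0.2 = 0.671, giving odds of at least one exacerbation 0.329/0.671 = 0.489. Untreated odds are exp(0.5) − 1 = 0.649. OR = 0.489/0.649 = 0.75. Simulation with 2,000,000 patients per scenario gave 0.753 to 0.757 for this case, and over all scenarios:

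| RR after therapy | Apparent OR (≥1 vs 0) when the true OR is 1.0 |
|---|---|
| 0.6 | 0.70 to 0.77 |
| 0.8 | 0.84 to 0.88 |
| 1.0 | 1.0 |
| 1.25 | 1.15 to 1.22 |
| 1.5 | 1.30 to 1.43 |

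This leaves out exacerbations at the prescribing visit itself.

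**4. Effect on an mMRC odds ratio.** Assumed: 40% of patients at mMRC ≥2, 60% treated below the cut, true OR 1.40. Treatment odds are 1.5 below the cut and 1.5 × 1.40 = 2.1 above it. Cells: ≥2 treated 0.4 × 2.1/3.1 = 0.271, untreated 0.129; <2 treated 0.36, untreated 0.24. Suppose treatment moves some treated breathless patients below the cut before the score is recorded:
- 5%: (0.257/0.129)/(0.374/0.24) = 1.28
- 10%: (0.244/0.129)/(0.387/0.24) = 1.17
- 15%: (0.230/0.129)/(0.401/0.24) = 1.07

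**5. Where it enters.** The chi-square and univariable comparisons of diagnosis cohorts contain no mMRC, lung or comorbidity value. Only cohort odds ratios adjusted for those variables can be affected.

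**The case against.** Several points on the other side stand.

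- **The subgroup first treated on the diagnosis date.** For these patients the year before diagnosis lies before treatment, so the order for exacerbations is largely restored, except for same-day events. It does not help the nearest-record variables, and the all-patients analysis stays exposed.
- **Reach of the nearest record.** With data to 2013, a reader might infer that values 12 to 16 years after diagnosis (2013 minus 2001 and 1997) could be used for every predictor in the earliest cohort. The documents do not support that for lung grade: eligibility ensures a spirometry record within the 5-year window, so the nearest one cannot lie further off than 2.5 or 5 years, depending on how the window is read. For mMRC and comorbidities no limit is stated, but those figures are only a ceiling, because the rule picks the smallest distance.
- **The time comparison.** A reader might infer that the comparison of cohorts is contaminated as a whole. It is not: the unadjusted comparison is untouched, and the exacerbation window is the same in each cohort.
- **Possibility, not fact.** Post-treatment values can enter; the documents do not show how often. A late code for a long-standing condition such as asthma may still describe the patient at the decision, and an exacerbation at the prescribing visit may be a genuine reason for it. The protocol itself speaks of potential predictors.
- **An unseen SAP might add a direction rule for the nearest record.** It could, but Appendix 1 already fixes the exacerbation window and states the nearest-record rule, so the protocol text needs changing in any case.

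Section 2.2 also calls the two years after diagnosis the outcome period, although it defines initial therapy in the baseline year. The two statements should be reconciled. If therapy were measured after diagnosis, the exacerbation overlap would vanish, but the nearest-record problem would remain.

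**Conclusion.** The point holds. As written, the protocol lets exacerbations that follow or coincide with the first prescription, and mMRC, lung grade and comorbidity values recorded after it, be analysed as its predictors. The overlap of the exacerbation and outcome windows is complete, and m/12 of that window is post-treatment for a first prescription m months before diagnosis.

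The direction and size of any bias cannot be read from the documents. The ranges shown (0.70 to 1.43 around a true 1.0 for exacerbations; 1.40 falling to between 1.28 and 1.07 for mMRC) rest wholly on assumed inputs, and there is no distortion from post-treatment events if therapy leaves the exacerbation rate unchanged. For scale only, the example odds ratios in Table 4 of Appendix 3 are 1.17 to 1.40 for mMRC, where shifts of this order would matter, and 2.33 to 4.62 for exacerbations, which lie outside the range that the assumed rate ratios produce from a true 1.0.

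The all-patients odds ratios, other than for year of diagnosis, age and gender, should therefore not be read as drivers of choice under the present definitions. Adjusted cohort odds ratios may also be affected.

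**What to change.** In Appendix 1:

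1. Set an index date: the first qualifying prescription in the baseline year, and for untreated patients a matched or assigned date drawn from the same distribution of days before diagnosis.
2. Count exacerbations strictly before the index date, with equal look-back in both groups or as a rate per observed person-time. Only one pre-diagnosis year is guaranteed. A full 12 months before a prescription 3, 6 or 9 months ahead of diagnosis would need records back to 15, 18 or 21 months. Ending the window at diagnosis for untreated patients but earlier for treated ones would create a new imbalance.
3. Accept asthma and other comorbidities only if coded on or before the index date, or at the latest on or before diagnosis.
4. Use the last mMRC and spirometry value on or before the index date. Keep the nearest-record values as a sensitivity analysis. The spirometry eligibility rule need not change.

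In section 5.4, make the subgroup first treated on the diagnosis date the main basis for statements about drivers, with untreated patients as its stated comparison group, predictors dated on or before diagnosis, and same-day exacerbations excluded. Otherwise report the all-patients odds ratios as associations only.

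Cost: new wording and a re-extraction from the same records. There will be more missing mMRC and spirometry values, a shorter exacerbation look-back for some patients treated before diagnosis, and the loss of same-day exacerbations that may have been true triggers.

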3.2 Data source

The study will use patient data from the Optimum Patient Care Research Database (OPCRD). The study team work with fully anonymised data, removed of any patient identifiable information. The OPCRD is developed, maintained and owned by Optimum Patient Care, a social enterprise company that aims to improve patient outcomes through medical research and services. OPC provides evidence based recommendations to UK general practices through bespoke software and practice reports.

The OPCRD currently comprises longitudinal medical records for over 2.2 million patients from over 550 primary care practices across the UK. The OPCRD contains two types of data:

- routinely recorded clinical data and
- questionnaire responses from over 40,000 respiratory patients.

The OPC questionnaires are a compilation of validated questions covering symptoms, disease control, triggers, side effects, quality of life and unique adherence measures. Indeed the OPCR is the only database in the UK which compliments routinely recorded disease coding and prescribing information with patient reported outcomes. OPCR also links with nationwide practice prescribing data to enable targeted delivery of dataset needs.

The database has received a favourable opinion from the Health Research Authority for clinical research use (REC reference: 15/EM/0150). It is governed by The Anonymous Data Ethics Protocols and Transparency (ADEPT) committee, an independent body of experts and regulators commissioned by the Respiratory Effectiveness Group (REG) to govern the standard of research conducted on internationally renowned databases. All research using OPCR will be registered on recognised study databases such as the European Network of Centres for Pharmacoepidemiology and Pharmacovigilance (ENCePP).

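### The mMRC rule has no maximum distance from diagnosis, so the lag it permits differs by diagnosis period, which is itself a predictor in the same models

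*Protocol*

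**What the plan says.** Appendix 1 (section 12.1) describes the score as "Combined mMRC score from either routine medical notes or questionnaire data if available". Its time period is the reading "closest to date of COPD diagnosis". No maximum distance is given, and nothing says whether the reading must come before or after diagnosis.

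Two neighbouring variables are bounded. The exacerbation rate is "Calculated during the year prior to and including the date of COPD diagnosis", and section 3.1 requires "Spirometry data supportive of a COPD dx in the 5 year window around date of diagnosis".

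On calendar time, section 2.2 says "The data utilised in this study ranges from 1997" and runs to 2013. It divides patients by diagnosis date into 1997-2001, 2002-2006 and 2007-2010, and gives the purpose: "Cohorts will be chosen to assess how prescription patterns have changed over time".

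Section 5.4 lists diagnosis period, mMRC and GOLD group (B vs A, D vs C, A+B vs C+D) among the main potential predictors. For each of the two outcomes it plans univariable models and "a multivariable logistic regression model with stepwise reduction to derive best-fitting model of non-collinear predictors". Appendix 1 does not define GOLD A-D, but mMRC is the only symptom score in its variable list.

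**The concern.** Initial therapy is what was prescribed in the year before and at diagnosis (section 2.2). To explain that choice, a breathlessness score should describe the patient at about that time. A nearest-reading rule without a limit does this only if readings were made near diagnosis, and to the same degree in every cohort.

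The rule leaves far more room for late scores in the early cohort than in the late one. If that room was used, mMRC would mean breathlessness at diagnosis in 2007-2010 and, for some patients, breathlessness years later in 1997-2001. A model holding both period and mMRC would then mix a change in measurement with a change in prescribing. The odds ratios at stake are those for mMRC, for the GOLD contrasts if the groups use mMRC, and for period after adjustment.

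**Working it through.** The protocol gives no figure for mMRC coverage or lag, so there is none to reproduce.

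**Step 1: lag permitted by the rule.** Inputs from section 2.2: cohort limits, and data to 2013 (taken as the end of that year). Longest lag = end of data − diagnosis date.

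| Cohort | Diagnosed on last day | Diagnosed on first day |
|---|---|---|
| 1997-2001 | end 2013 − end 2001 = 12 years | end 2013 − start 1997 = 17 years |
| 2002-2006 | end 2013 − end 2006 = 7 years | end 2013 − start 2002 = 12 years |
| 2007-2010 | end 2013 − end 2010 = 3 years | end 2013 − start 2007 = 7 years |

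The smallest ceiling in the early cohort (12) exceeds the largest in the late cohort (7) by 5 years. These are ceilings; a patient whose record ends sooner has a lower one. If data truly start in 1997 and a prior year is required, the first eligible diagnosis is in 1998 and 17 becomes 16.

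**Step 2: comparison with other predictors.** Exacerbations are confined to one year. Lung function grade also uses the nearest reading, but eligibility requires supporting spirometry within a 5-year window, so a reading near diagnosis should exist. No criterion does this for mMRC.

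**Step 3: what the lag could be.** The protocol does not date the start of mMRC recording, so the start year is an assumption, with diagnoses spread evenly within cohorts. Share = proportion of diagnosis dates t with t + 1 ≥ start. Mean minimum lag = mean of max(start − t, 0).

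| Assumed start | Share able to have a reading within 1 year (early / middle / late) | Mean minimum lag, early | Mean minimum lag, late |
|---|---|---|---|
| 1997 or before | 100% / 100% / 100% | 0 | 0 |
| 2000 | 60% / 100% / 100% | 0.9 years | 0 |
| 2003 | 0% / 100% / 100% | 3.5 years | 0 |
| 2005 | 0% / 60% / 100% | 5.5 years | 0 |
| 2007 | 0% / 20% / 100% | 7.5 years | 0 |
| 2009 | 0% / 0% / 75% | 9.5 years | 0.5 years |

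Examples: for 2000, (2002 − 1999)/5 = 60% and (3²/2)/5 = 0.9; for 2005, 2005 − 1999.5 = 5.5. Any start of 2003 or later gives 0% in the early cohort by construction.

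**Step 4: effect of late scoring in the early cohort only.** Assumptions: equal cohorts, 40% symptomatic in each, log-odds of treatment 0.3 without symptoms, true period odds ratio 1.00, no error in the late cohort. In the early cohort, sensitivity is 0.9 and specificity 0.8 or 0.6, since some patients become breathless after diagnosis. A logistic model was fitted to the expected cells.

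| True symptom OR | Specificity, early | Fitted period OR (late vs early) | Fitted symptom OR |
|---|---|---|---|
| 1.4 | 0.8 | 1.02 | 1.32 |
| 1.4 | 0.6 | 1.05 | 1.28 |
| 3.0 | 0.8 | 1.07 | 2.43 |
| 3.0 | 0.6 | 1.17 | 2.18 |

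The largest mMRC odds ratio in example Table 4 is 1.40, so the first two rows are nearer to what that table illustrates.

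**Step 5: effect if patients without a score were left out.** The late-vs-early odds ratio is multiplied by (late treated × early untreated)/(late untreated × early treated), where each term is an assumed probability of having a score.

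- Recording unrelated to treatment: (0.80 × 0.30)/(0.80 × 0.30) = 1.00
- Mild dependence in the early cohort: (0.80 × 0.25)/(0.75 × 0.35) = 0.76
- Stronger dependence: (0.80 × 0.20)/(0.70 × 0.40) = 0.57

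**The case against.** The strongest reply is that a permitted lag is not an actual lag. The protocol neither dates the start of mMRC or questionnaire recording nor gives completeness by cohort. If readings were common throughout, the nearest one lies close to diagnosis in every cohort and the missing limit does no harm. BMI, smoking status and the comorbidities also use the nearest record without a limit. All of this stands, and the point must be put as a risk.

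Four stronger readings are tempting, and the document supports none of them:

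- **Early patients lack a score or were scored years late.** Step 3 shows this follows only from an assumed late start.
- **The questionnaire reaches few patients.** Section 3.2 reports "questionnaire responses from over 40,000 respiratory patients" in a database of over 2.2 million, about 1.8%. But the smaller figure counts respiratory patients and the larger counts everyone. The COPD share is not given, and routine notes are the other source.
- **The early cohort reduces to survivors who stayed registered.** This needs patients without mMRC to be dropped. Handling of missing values may be settled in an analysis plan not shown here.
- **The cohorts are adjusted for mMRC.** Period, mMRC and GOLD group are only candidates, subject to stepwise reduction and a collinearity check. Mock Table 2 has no mMRC row, and example Table 4 has no period or GOLD row. The planned chi-square test and univariable odds ratio for period need no mMRC.

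What survives is the definition itself: a stated rule whose tolerance varies with a predictor under study.

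**Conclusion.** The point holds in limited form and is worth correcting. The differing ceilings (12-17, 7-12 and 3-7 years) follow from the protocol's own dates, assuming only that data run to the end of 2013. So does the fact that period, mMRC and GOLD group are candidates for the same models. That GOLD A-D uses mMRC is an inference, though a reasonable one.

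Whether any odds ratio is biased cannot be settled from the document. With a symptom odds ratio of 1.4, late scoring alone moves the period odds ratio to 1.02-1.05 and lowers the mMRC odds ratio to 1.32-1.28. The latter change is similar in size to the steps between grades in example Table 4 (1.17, 1.22, 1.26, 1.40). Selection could matter more (0.76 or 0.57), but only if patients without a score are omitted and recording depends on treatment differently by era; otherwise the factor is 1.00.

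A reader might infer that the period comparison is invalid or that the early cohort must be excluded. Neither follows. The mock tables as drawn would not reveal a problem, however: Table 2 has no mMRC row, Table 3 has no row for missing values, and section 5.3 lists percentage non-missing only for interval or ratio variables.

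**What to change.** 1. **Appendix 1.** Accept an mMRC reading only within one fixed window around diagnosis, the same for all cohorts (12 months, for example), and otherwise code it missing. Where GOLD A-D uses mMRC, derive it only from such readings, and state its definition.
2. **Mock Table 2.** Add, by cohort, the percentage with an in-window mMRC and the lag between diagnosis and reading. This shows whether the risk is real.
3. **Section 5.4.** For each outcome, also report the period odds ratios from a multivariable model in all eligible patients without mMRC and GOLD group, beside the model that includes them. Agreement would be reassuring; a gap would show that the period result depends on how breathlessness was recorded or adjusted for.

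This takes protocol wording, two table entries and one more model per outcome, with no new data. The window leaves fewer patients and wider intervals for the mMRC and GOLD odds ratios, perhaps very few in 1997-2001. The added period model does not adjust for breathlessness, so it should accompany the fuller model and not replace it. The 12-month figure is a choice; any width fixed in advance and common to all cohorts meets the point.

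### The asthma flag has no direction or time limit, so it admits codes recorded after the outcome, and the room for such codes differs by diagnosis cohort

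*Protocol*

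**What the plan says.** Protocol Appendix 1 (section 12.1) defines asthma as "Presence / absence of a co-morbid diagnosis of Asthma in routine medical notes". The time-period column reads "closest to date of COPD diagnosis". Rhinitis, reflux disease, heart failure, diabetes and the other comorbidities have the same form. None has a direction (before or after) or a largest permitted distance.

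The outcome is timed differently. Section 2.2 states: "COPD initial therapy will be defined as pharmacological therapy prescribed during one year prior to and at the initial date of COPD diagnosis".

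Section 2.2 also fixes the calendar: "The data utilised in this study ranges from 1997 – 2013". Appendix 1 defines the cohorts: "Year of first COPD diagnosis split into three cohorts: 1997 -2001, 2002 - 2006, 2007 - 2010". Eligibility requires one year of data before diagnosis and two years after it.

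Section 5.4 lists asthma among the main potential predictors and, for both outcomes, gives it two further roles: "Presence of co-morbid asthma diagnosis used both as adjustment and as stratification variable (two multivariable models".

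Other variables in the protocol are bounded. The exacerbation rate uses the year ending on the diagnosis date, and supporting spirometry must fall in a five-year window around diagnosis.

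**The concern.** Taking the nearest record suits a measured value such as BMI. It suits a yes/no flag badly, because absence has no date. Without a limit, a code entered years after COPD diagnosis can make a patient asthmatic for the analysis.

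Two things follow. First, such a code postdates the prescribing decision it is meant to predict or adjust for, and may even have been influenced by the treatment given. This applies in every cohort. Second, the time available for such codes depends on diagnosis year, and diagnosis cohort is itself a predictor under comparison. The flag can then mean mainly asthma known at diagnosis in one cohort and include much later labelling in another. The study asks how predictors change over time, so a shift in the meaning of asthma could be read as a change in prescribing.

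**Working it through.** The protocol gives no asthma prevalence, coding rate or sample size, so it has no figure of its own to reproduce.

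**1. Time available before and after diagnosis.** Take the data as 1 January 1997 to 31 December 2013 (17 years), diagnoses spread evenly within each cohort, and a full record for every patient. If m is the mean diagnosis date, look-back is m − 1997, look-forward is 2014 − m, and the forward share is (2014 − m)/17.

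| Cohort | m | Back (years) | Forward (years) | Forward share |
|---|---|---|---|---|
| 1997–2001 | 1999.5 | 2.5 | 14.5 | 85% |
| the same, starting 1998 | 2000.0 | 3.0 | 14.0 | 82% |
| 2002–2006 | 2004.5 | 7.5 | 9.5 | 56% |
| 2007–2010 | 2009.0 | 12.0 | 5.0 | 29% |

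The 1998 row allows for the required prior year, which a 1997 diagnosis cannot have in full within data starting in 1997. A patient with only the minimum record (one year back, two forward) has a forward share of 2/3 = 67% in any cohort.

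**2. Illustration with no true period effect.** Assumptions, none of them protocol facts: true asthma prevalence 30% in every cohort; 60% treated without asthma; existing asthma re-coded at 0.5 per year; new asthma codes after diagnosis, unrelated to treatment, at 1% a year in the rest; a code anywhere in the 17 years counts. The asthma odds ratio of 3.88 is borrowed from mock Table 4, which is an example of layout.

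- Treated without asthma: odds 0.60/0.40 = 1.5. With asthma: 1.5 × 3.88 = 5.82, or 85.3%.
- Existing asthma found: 1 − exp(−0.5 × 17), practically 100%.
- Falsely flagged: 1 − exp(−0.01 × forward years) = 13.5%, 9.1%, 4.9%.
- Apparent prevalence: 0.30 + 0.70 × false share = 39%, 36%, 33%.
- Treated among the flagged, early cohort: (0.30 × 0.853 + 0.70 × 0.135 × 0.60)/0.394 = 79.3%, odds 3.82, asthma odds ratio 3.82/1.5 = 2.55. The other cohorts give 2.83 and 3.20.
- Late versus early within the asthma stratum: 3.20/2.55 = 1.25. Without asthma it is 1.00.
- A logistic model of treatment on flag and cohort, fitted to the expected counts, gives an adjusted late-versus-early odds ratio of 1.06 (1.04 to 1.10 for 0.5% to 2% a year).

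**3. Dependence on the assumptions.** Now let all asthma arise as first codes within the data, at one annual rate before diagnosis and another after, with the early cohort starting in 1998. Apparent prevalence by cohort is then:

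| Rate before / after | 1998–2001 | 2002–2006 | 2007–2010 |
|---|---|---|---|
| 2% / 2% | 28.8% | 28.8% | 28.8% |
| 2% / 1% | 18.1% | 21.7% | 25.2% |
| 1% / 2% | 26.7% | 23.3% | 19.7% |

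Prevalence can be equal or move either way. Even in the equal case, the share first coded after diagnosis is 80%, 52% and 26%. If 3.88 applies only to asthma coded before diagnosis, later-coded asthma has odds ratio 1, and 50% or 70% are treated without asthma, the rates 2%/2%, 2%/1% and 2%/0.5% give asthma odds ratios of about 1.2–1.8 early and 2.4–3.4 late. The false late-versus-early odds ratio in the asthma stratum is then about 1.9–2.1. This is a harsher set of assumptions than step 2.

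**4. Candidate remedies, under the step 2 assumptions.**

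- Any code before diagnosis: removes post-outcome codes but leaves look-back unequal. With 1–5 years of look-back in the first cohort, the false period odds ratio is 0.91 (0.86 to 0.97 for re-coding at 0.2 to 1.0 per year).
- One year before diagnosis: captures 1 − exp(−0.5) = 39% of asthma, so apparent prevalence is 0.39 × 30% = 12%. The asthma odds ratio is 3.10 in every cohort and the period odds ratio is 1.00. If re-coding instead rises from 0.2 to 0.5 to 1.0 per year across cohorts, prevalence is 5%, 12%, 19% and the period odds ratio is 0.88.

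**The case against.** The strongest reply is that bias is only possible. With full records every cohort has the same 17-year total, and step 3 shows a case with no prevalence drift and others where it goes either way. This stands. A reader might infer that the rule must create false period differences; the documents do not support that.

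A reader might also infer that early-cohort asthma codes mostly fall after diagnosis. The shares in step 1 describe available time under complete records, not where codes lie, and eligibility guarantees only one year before and two after. That stands too.

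Third, the time-period label can be read as status around diagnosis, and exact windows may be left to a SAP that is not shown. This stands in part. That any code anywhere counts is an assumption of the illustration, and the protocol does not say so. But the entry is a stated definition in the protocol's variable list, it permits later codes on its face, and the same list bounds exacerbations.

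Finally, a one-year flag is insensitive and equalises ascertainment only if re-coding is stable. Section 2.2 itself names the 2004 introduction of QoF as a possible influence on prescribing, so stable coding cannot be taken for granted. This stands and limits the remedy.

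**Conclusion.** The concern holds in a limited form. What needs no modelling is that the stated rule lets asthma and comorbidity codes made after the outcome serve as predictors, adjusters and, for asthma, the stratifier. The cohort contrast in available time follows from the protocol's dates, provided records are near complete and none of the asthma entries used predates 1997.

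The effect on estimates is a possibility of unknown size and direction. In the main illustration it is small for the adjusted period effect (1.04–1.10) and larger for the asthma odds ratio (2.55 to 3.20 across cohorts, against an assumed 3.88) and for the asthma stratum (1.25). Harsher assumptions give more. The odds ratios of 0.91 and 0.88 in step 4 belong to alternative rules and are not biases of the protocol's own definition.

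The definition should be changed before analysis; nothing here shows that the study's results would be wrong.

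**What to change.** In Appendix 1, count asthma and the other comorbidities only from codes on or before the COPD diagnosis date, with a look-back of the same length in every cohort. One year is the only history that eligibility guarantees, and it matches the exacerbation window. Use this flag for adjustment and stratification. Repeat the adjusted and asthma-stratified models with any code before diagnosis, and report asthma prevalence by cohort under both definitions.

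The cost is one changed definition and one further set of runs on data the study already needs. The downside is that a one-year window misses asthma not re-coded in that year and is comparable across cohorts only if re-coding is stable. A period effect should therefore be interpreted only if it is consistent under both definitions. Agreement is necessary but not sufficient: step 4 shows that both can err in the same direction, which is why prevalence by cohort should be shown beside the models.
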